4.1. Sample Size

The trial is powered for detecting superiority of balixafortide + eribulin versus eribulin monotherapy for the primary efficacy endpoint of PFS in the 3^{rd} line+ population.

In the trial, patients will be randomized in a 1:1 ratio to the two treatment arms stratified by line of therapy (2nd line versus 3rd line+), hormone receptor status (positive versus negative), prior treatment with CDK 4/6 inhibitor (received a CDK 4/6 inhibitor versus not received a CDK 4/6 inhibitor) and visceral versus non-visceral disease.

The sample size calculations are event-driven. In the 3rd line+ population, approximately 320 patients are required in order that 286 PFS events occur within 24 months of randomizing the first patient. Patients who discontinue from the study will not be replaced.

The sample size calculations were based on the following assumptions:

- Overall 1-sided type I error rate: 0.020;
- In the 3rd line+ population, a median PFS on eribulin monotherapy of 3.9 months vs 5.8 months for balixafortide + eribulin to give a PFS hazard ratio 0.674;
- Power of 90%;
- Assuming a 12-month non-linear recruitment period ($\eta=2$; Carroll, 2009) and a minimum 12-month follow-up period after the last patient is randomized.
- Further, assuming a median OS on eribulin monotherapy of 14.4 months vs 17.4 months for balixafortide + eribulin to give an OS hazard ratio 0.828, a total of 226 deaths are expected in the 3rd line+ population in the final analysis of OS, planned to take place 12 months after the PFS analysis. Note, there is only one formal analysis of PFS to take place once 286 PFS events have accrued. No further formal analyses of PFS are planned.

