8.1.1. Progression-Free Survival

PFS, as assessed by the IRC, is a co-primary efficacy endpoint in the 3^{rd} line+ population. The RECIST v1.1 guidelines will be used to determine disease progression. The alpha allocation will be 0.040 2-sided. From the date of randomization, patients will be evaluated for PD based on blinded, central review of CT/MRI scans as described in Section 8. Patients who discontinue study treatment prior to PD will undergo repeat CT/MRI scans and tumor response assessments every 8 weeks (\pm 7 days) for the first year post randomization and 12 weeks (\pm 7 days) after the first year post randomization, regardless of regimen, until confirmed PD is documented, death occurs, patient is lost to follow-up, or the patient withdraws consent (whichever occurs first).

Date of Progression will be the date assessed by the IRC.

PFS is defined as the time from the date of randomization to the earliest evidence of documented PD or death from any cause. Patients who are alive without documented PD or are either lost to follow-up or withdrew consent, will be censored at the date of last tumor assessment without disease progression.

The duration of PFS will be calculated as follows:

- For patients who have PD or died, Duration of PFS = Date of death/PD Date of randomization + 1 day;
- For patients who are alive without documented PD, Duration of PFS = Date of last tumor assessment (where response is not missing or unable to evaluate) Date of randomization + 1 day.

Table 1 below specifies the date of disease progression or censoring rules that will be carried out for the PFS analysis on the ITT (3rd line+) set:

Situation	Date of Disease Progression or Censoring	Outcome
No post-baseline assessments for tumor response and no death within first two tumor assessments	Date of randomization	Censored
Disease progression or death after two or more consecutive missed tumor response assessments	Date of last scan for tumor assessment showing no evidence of disease progression that is before the first missed visit	Censored
Not known to have progressed or died according to data in the database as of data-cut-off	Date of last scan for tumor assessment showing no evidence of disease progression	Censored
Disease progression reported on multiple response assessments	Earliest Date of Progression	Progressed
Disease progression or death after one missed tumor response assessment	Earliest Date of Progression	Progressed
Death without PD	Date of death	Progressed

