Starting anti-cancer therapy prior to observing PD or in absence of PD	Date of last scan for tumor assessment showing no evidence of disease progression prior to start date of the anti-cancer therapy	Censored

Table 1 - Date of Progression or Censoring for Progression-free Survival

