14.2. Type I Error Control for Primary and Key Secondary Efficacy Analyses

Figure 1 - Type I Error Control for Primary and Key Secondary Efficacy Analyses in the 3rd line+ patient population

			t	ORR est at a;=0.001					
		+ve	-				-ve	-	
		3rd line+ PFS test a OS at interim test a	t a;=0.040 t a;=0.002				3rd line-t PFS test at OS at interim test at	CL=0.040 t CL=0.001	
Г	3rd line -ve @ a	+ PFS a;=0.040	3rd line+ PFS +ve @ a;=0.040	_	Γ	3rd line -ve @ a	+ PFS =0.040	3rd line+ PFS +ve@ CL=0.040	-
	Overall PFS not	PopIn tested	overall PopIn test at a;c0.040	_	30	Overall PFS not	- PopIn tested	Overall PopIn test at a;=0.040	-
┝	nterim OS-ve	Final OS test @ a=0.008	Overall PopIn PFS-ve and Interim OS-ve	Final OS test at a;:0.008		Interim 05-ve	Final OS test @ a.=0.008	Overall PopIn PFS-ve and Interim OS-ve	Final OS test ata;=0.008
L	Interim OS+ve	Final OS test @ a=0.010	Overall PopIn PFS-ve and Interim OS+ve	Final OS test at CL=0.0111>		Interim OS+ve	Final OS test @ a.=0.009	Overall PopIn PFS -ve and Interim OS+ve	Final OS test at a=0.009
			Overall PopIn PFS+ve andInterim OS-ve	Final OS test at CL=0.048				Overall PopIn PFS+ve and Interim 05-ve	Final OS test ata;=0.048
			Overall PopIn PFS+ve andInterim OS +ve	Final OS test at CL=0.050				Overall PopIn PFS+ve and Interim OS+ve	Final OS test at a;=0.049

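### The projection of 286 PFS events from about 320 patients by month 24 allows for no loss or censoring, and the single event-triggered PFS analysis has no fallback if the count is not reached

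*SAP*

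**What the plan says.** SAP 4.1 states that "approximately 320 patients are required in order that 286 PFS events occur within 24 months of randomizing the first patient". Its listed assumptions are the one-sided 0.020 alpha, 90% power, median PFS of 3.9 and 5.8 months, and a 12-month non-linear accrual (η=2) followed by at least 12 months of follow-up. No dropout or censoring rate is among them. The section adds that "Patients who discontinue from the study will not be replaced" and that "there is only one formal analysis of PFS to take place once 286 PFS events have accrued", with no further formal PFS analysis planned. SAP 8.3 and protocol 12.3.7.3 mention 12 months of minimum follow-up only as the time when the count is expected, not as an alternative trigger. Protocol 12.2.1 uses the same construction for the Overall Population: 346 events from 384 patients.

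The PFS rules in SAP 8.1.1 remove patients from the event count. Those without documented progression who "are either lost to follow-up or withdrew consent, will be censored at the date of last tumor assessment without disease progression". Table 1 also censors patients with no post-baseline assessment (unless they die within the first two assessments), "Disease progression or death after two or more consecutive missed tumor response assessments", and "Starting anti-cancer therapy prior to observing PD or in absence of PD".

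The interim OS analysis takes place at the PFS analysis (SAP 8.3). SAP 4.1 describes final OS as "planned to take place 12 months after the PFS analysis", while SAP 8.3 sets it when all randomized patients have at least 24 months of follow-up.

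**The concern.** An event-driven trial can wait for events, but only while enough patients remain who can still have one. Here the margin between patients and required events is 34, and the plan's own censoring rules draw on it. Two things follow. First, the month-24 date holds only with no loss, so any censoring delays the PFS analysis. Second, the trigger is an event count alone. If the count cannot be reached, a literal reading leaves a co-primary endpoint untested and the interim OS analysis undone. The team would then have to choose a cut-off late in an open-label trial, which is better settled in advance.

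The fallback is missing from the documents supplied. SAP version 1.4 and the DSMB charter, both cited in the SAP, were not available. SAP 4.6 mentions possibly adjusting the sample size, but only in connection with COVID-19 and without a rule.

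**Working it through.** **Inputs.** All are from SAP 4.1: one-sided alpha 0.020, power 90%, HR 0.674, medians 3.9 and 5.8 months, 1:1 allocation, 12-month accrual with η=2 (read as cumulative accrual (t/12)²), 320 patients, 286 events. PFS is taken as exponential in each arm, with λ = ln 2 / median.

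**1. The event count reproduces.** d = 4(z₀.₉₈ + z₀.₉₀)² / (ln HR)² = 4(2.0537 + 1.2816)² / (0.39453)² = 285.9, so 286.

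**2. The patient number reproduces only with no loss.** The probability of an event by month 24 is the integral over t from 0 to 12 of (2t/144)·[1 − exp(−λ(24 − t))].

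- Eribulin 0.9348; combination 0.8442; mean 0.8895.
- 320 × 0.8895 = 284.6 events. For 286 events, 286/0.8895 = 321.5 patients.
- With 320 patients, the 286th event is expected at month 24.3.

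The same zero-loss model comes close to two other stated figures. OS medians of 14.4 and 17.4 months give 225.3 deaths at month 36 (SAP 4.1: 226). Medians of 3.9 and 5.6 months give 343.4 events from 384 patients (protocol 12.2.1: 346). That no allowance was made is an inference, but three figures support it.

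**3. The ceiling is a count and needs no model.**

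- 320 − 286 = 34, and 34/320 = 10.6%.
- Overall Population: 384 − 346 = 38, and 38/384 = 9.9%. Protocol 12.2.7.1 has a narrower censoring rule there.
- If 330 were enrolled: 330 − 286 = 44, and 44/330 = 13.3%.

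**4. Timing and power under assumed censoring.** The documents give no rate, so these shares are assumptions. Two models are shown as A / B. In A, exponential censoring with the same hazard g in both arms is set so that the mean of g/(λ+g) equals the share. In B, a fixed share never yields an event. Power = Φ(½√d × 0.3945 − 2.054).

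| Share never yielding an event | Events at month 24 | Month of 286th event |
|---|---|---|
| 0% | 284.6 | 24.3 |
| 2% | 280 / 279 | 25.3 / 25.7 |
| 5% | 274 / 270 | 27.5 / 28.6 |
| 8% | 268 / 262 | 31.9 / 34.2 |
| 10% | 263 / 256 | 41.0 / 45.2 |
| above 10.6% | – | never |

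In model A, the 10.6% ceiling corresponds to g = 0.0171 per month, which is 1 − exp(−12 × 0.0171) = 18.5% loss per year.

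A cut-off at month 30 would give:

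| Share | Events at month 30 | Power |
|---|---|---|
| 10% | 278 / 274 | 89.2% / 88.7% |
| 15% | 264 / 259 | 87.6% / 86.8% |
| 20% | 250 / 243 | 85.7% / 84.7% |
| 25% | 236 / 228 | 83.5% / 82.3% |

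Up to a share of 7.0% / 6.0%, the 286-event trigger still fires before month 30.

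**5. Sensitivity to accrual.** Uniform accrual would give 291.9 zero-loss events at month 24. That is enough at 2% censoring (287.4 / 286.1) but not at 5% (280.5 / 277.3). The ceiling of 34 does not change.

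**6. OS.** In the SAP 14.2 figure, the 0.040 passes to final OS only after PFS succeeds in both the 3rd line+ and Overall populations. Without a PFS test, final OS stays on the branch "Final OS test @ a=0.008". Zero-loss deaths are 160.1 at month 24, 197.0 at month 30 and 225.3 at month 36.

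**The case against.** The strongest reply is that nothing here is miscalculated. The figures agree with each other, power is 90% whenever 286 is reached, and waiting for events is how this kind of design absorbs loss. Any trial needing d events from N patients fails if more than N − d never have one, so the ceiling says little without a censoring rate, and the documents give none. Loss of about 18.5% per year is substantial. The plan also works against it: patients who stop treatment stay on study (protocol 5.3.1), imaging continues until progression (protocol 7.8.1), loss to follow-up must be pursued (protocol 5.3.2), and death without progression counts as an event (SAP 8.1.1, Table 1). The SAP says approximately 320, so slight over-enrolment is possible.

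Most of this stands. It limits the point to a missing allowance and a missing fallback rule, and leaves the likelihood of reaching the ceiling unknown. It does not rescue the month-24 projection under the stated η=2 accrual, and it supplies no rule for a stalled count.

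Two stronger readings are tempting. A reader might infer that a stalled PFS trigger also stalls final OS. It does not: SAP 8.3 fixes final OS by calendar follow-up, and the PFS-relative wording elsewhere is planning text that conflicts with it only if PFS is late. A reader might also set OS power of 28.8% at alpha 0.048 against 10.9% at 0.008 (HR 0.828, 226 deaths) and call the difference the cost. The 0.048 exists only after PFS has succeeded in both populations, so this compares a post-success branch with the floor. The trial is powered for PFS, not OS.

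**Conclusion.** The point holds as a planning gap that should be fixed. The month-24 event count is a zero-loss projection presented without that label, while the SAP's own rules censor several groups. Under the planned hazards and accrual, an assumed 5% censoring moves the PFS analysis to about month 27.5 to 28.6, and 10% to about month 41 to 45, beyond the 36-month trial duration in SAP 3.1. With 320 enrolled, more than 34 patients without a countable event means that the PFS analysis is never triggered, the interim OS analysis is not performed, and final OS is tested at its floor of about 0.008.

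A reader might infer that the trial is underpowered, that 286 or 320 is wrong, or that Type I error is inflated. The documents support none of these. Nor do they show that the 10.6% ceiling will be exceeded. The ceiling itself is exact for 320 patients. The timings rest on exponential PFS, the stated medians, η=2 and the assumed censoring shares.

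**What to change.** Add no patients.

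1. In SAP 4.1 and protocol 12.2.1 and 12.3.1, label 286 (and 346) events by month 24 as a zero-loss projection. State expected events, timing and power over a range of assumed censoring.
2. Keep the event trigger at two-sided alpha 0.040 and add a calendar long-stop for the single PFS analysis, whichever comes first. Place it clearly before final OS so that interim and final OS remain separate, for example 18 months after last randomization (about month 30). It should be set from pooled event counts by people without access to arm-level results. This matters because the formal ORR analysis is scheduled before PFS and may already have been unblinded.
3. Make the SAP 8.3 rule, at least 24 months of follow-up for all randomized patients, the only timing rule for final OS. Remove the PFS-relative wording in SAP 3.1, SAP 4.1 and protocol 12.2.7.3. With a month-30 PFS analysis, a further 12 months would mean month 42, against month 36 under the 24-month rule.

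The cost is a SAP and protocol amendment. If the long-stop is used, PFS power is about 88.7% to 89.2% at 10% censoring and 82.3% to 83.5% at 25%. The interim OS analysis moves from about 160 to about 197 expected deaths. Its alpha is a separate additive share, so Type I error is unaffected.

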4.2. Randomization, Stratification, and Blinding

This trial is an open-label, randomized, parallel, two-arm, multicenter, international Phase III trial. Patients will be randomized after the investigator has verified eligibility.

Patients will be randomized in a 1:1 ratio to one of the following treatment regimens:

• Balixafortide + eribulin

or

• Eribulin monotherapy

- Line of therapy (2nd line vs 3rd line+).
- HR receptor status (positive vs negative).
- Prior treatment with Cyclin-dependent kinase (CDK) 4/6 inhibitor (received a CDK 4/6 inhibitor vs not received a CDK 4/6 inhibitor).
- Visceral vs non-visceral disease.

For stratified analyses in the 3rd line+ population, the stratification factors (HR receptor status at randomization, prior CDK 4/6 inhibitor treatment and visceral disease) entered into the Interactive Response Technology (IRT) at the time of randomization will be used in analysis models. The randomization strata will be summarized by treatment arm for the Intention-to-treat (ITT) set, Line of therapy (only applicable in 2nd line population), HR receptor status, prior treatment with CDK 4/6 inhibitor (yes, no) and visceral disease (yes, no). Additionally, the exact line of therapy, as captured on the CRF, will also be summarized.

The analyses by line of therapy will be done on data collected in IRT system and imported as such in eCRF. The exact number of lines of therapies is collected in eCRF and will be used to summarize any discrepancy with the stratification factor.

The block size will be pre-specified and implemented in the IRT and will not be known to the Investigator. Polyphor Ltd. will determine the maximum number of patients that can be enrolled at each participating site and/or each geographic region.

4.3. Analysis Set

For the Food and Drug Administration (FDA) submission, the following analysis sets have been defined: Intent-to-Treat (3rd line+), Intent-to-Treat (3rd line+ confirmed), Per-Protocol (3rd line+ confirmed), Response Evaluable (3rd line+), Response Evaluable (3rd line+ confirmed), Patient Reported Outcome (3rd line+), Safety (3rd line+) in the 3rd line+ population. Note that the 3rd line+ population in these sets refers to those who were randomized as 3rd line+. 3rd line+ Confirmed refers to the subset of patients stratified as 3rd line+ who were confirmed as receiving the investigational medication as 3rd line of therapy or more in the eCRF data.

The efficacy endpoints analysis will be conducted in the ITT sets: Intent-to-Treat (3rd line+) for PFS and OS and Response Evaluable (3rd line+) for ORR. The other additional sub-sets defined in this section Intent-to-Treat (3rd line+ Confirmed), Per-Protocol (3rd line+ Confirmed) and Response Evaluable (3rd line+ Confirmed) will be used for sensitivity analysis.

In addition, the following analysis sets will be of interest for submissions to all regulators: Enrolled, Intent-to-Treat and Safety for the overall population.

4.3.1. Enrolled Set

Enrolled set is defined as all screened patients of the overall population who signed the informed consent.

4.3.2. Intent-to-Treat Set

The Intent-to-treat (ITT) set is defined as all randomized patients in the overall population. The co-primary endpoint PFS will be analyzed in this set if it is found to reach significance in the ITT $(3^{rd} line+)$ set as described in Section 8.3 and Figure 1.

4.3.3. Intent-to-Treat Set (3rd Line+)

The Intent-to-treat (ITT) set (3^{rd} line+) is defined as all randomized patients in the 3^{rd} line+ population. The 3^{rd} line+ population is defined in the study as patients allocated to the 3^{rd} line+ randomization strata. Efficacy data in this analysis set will be summarized by randomized treatment. The co-primary endpoint PFS, key secondary efficacy endpoint OS and exploratory efficacy endpoints will be analyzed by the treatment arm to which they are randomized using ITT (3^{rd} line+).

4.3.4. Intent-to-Treat Set (3rd Line+ Confirmed)

The ITT set $(3^{rd} \text{ line+ confirmed})$ includes only those ITT (3^{rd} line+) patients confirmed as receiving the investigational medication as 3^{rd} line of therapy or more, as per eCRF data. Note that this analysis set therefore **excludes** patients randomized in 3^{rd} line+ but receiving the investigational medication as only the 1^{st} line or 2^{nd} line of therapy as per eCRF.

A sensitivity analysis will be conducted on the co-primary endpoint PFS and the key secondary efficacy endpoint OS using the ITT set (3^{rd} line+ Confirmed). Patients will be analyzed by the treatment arm to which they are randomized.

4.3.5. Per-Protocol Set (3rd Line+ Confirmed)

The Per-Protocol (PP) set (3rd line+ confirmed) is defined as a subset of the ITT set (3rd line+ confirmed), including only patients who took at least one dose of Eribulin and without any major protocol deviation that could affect the evaluability of the co-primary efficacy endpoints. Protocol deviations causing the exclusion of patient from PP set are listed in the Study Deviations Rules document.

A sensitivity analysis will be conducted on the PFS and the key secondary efficacy endpoint OS using the PP set (3^{rd} line+ confirmed). Patients will be analyzed by the treatment arm to which they are randomized.

4.3.6. Response Evaluable Set (3rd Line+)

The Response Evaluable (RE) set (3rd line+) will be used to evaluate disease response. The RE set (3rd line+) includes all randomized patients in the 3rd line+ population with measurable disease by RECIST v1.1 as determined by the Investigator at screening during the evaluation of breast cancer history. The co-primary endpoint analysis of ORR and other secondary endpoint analyses of CBR, duration of response, DCR and time of response will be conducted using the RE (3rd line+) set. Patients will be analyzed by the treatment arm to which they are randomized.

4.3.7. Response Evaluable Set (3rd Line+ Confirmed)

The Response Evaluable (RE) set $(3^{rd} \text{ line} + \text{ confirmed})$ is a subset of RE set $(3^{rd} \text{ line} +)$ including only those patients confirmed as receiving the investigational medication as 3^{rd} line of therapy or more, as per eCRF data.

A sensitivity analysis will be conducted on the co-primary endpoint ORR using the RE set $(3^{rd}$ line+ confirmed)

4.3.8. Patient Reported Outcome Set (3rd Line+)

The Patient Reported Outcome (PRO) set $(3^{rd} line+)$ is defined as all randomized patients in the $3^{rd} line+$ population where the patient has at least one post-baseline PRO value (e.g. EORTC

questionnaire, EQ-5D or FACT-B). Patients will be analyzed by the treatment arm to which they are randomized.

4.3.9. Safety Set

The Safety set consists of all randomized patients in the overall population who receive at least one dose (or partial dose) of study treatment (i.e. a subset of ITT).Patients will be analyzed by the treatment received, based on the first dose of study drug, to summarize the safety data overall. They will be included in the balixafortide + eribulin arm if they received at least one dose of balixafortide during the study.

4.3.10. Safety Set (3rd Line+)

The Safety set $(3^{rd} line+)$ consists of all patients from the ITT set $(3^{rd} line+)$ who receive at least one dose (or partial dose) of study treatment. Patients will be analyzed by the treatment received, based on the first dose of study drug. They will be included in the balixafortide + eribulin arm if they received at least one dose of balixafortide during the study.

4.4. Handling of Missing or Partial Date Data

Missing date data will be handled as follows:

- For prior cancer therapies and medical history of cancer, the study day corresponding to the start and stop date will be imputed prior to calculating duration of the therapy/history using the following rules:
 - For partially missing start dates, missing day of the month will be imputed as the first of the month and missing month will be imputed as January. No imputation will be done if the year is missing.
 - For partially missing stop dates, missing day of the month will be imputed as the last day of the month and missing month will be imputed as December and at least 1 day after the start date of the therapy/history. Any imputed date occurring after the screening visit date will be imputed to the screening visit date. No imputation will be done if the year is missing.
- For prior radiotherapy and surgery, the relevant time to the initiation of the trial, etc. will be calculated using the recorded date of radiotherapy or date of procedure for surgery. The imputation rules described for prior cancer therapies will be applied to prior radiotherapy and surgery.
- For time since initial diagnosis to informed consent and time since diagnosis of locally recurrent or metastatic disease to informed consent, partial dates for initial diagnosis and diagnosis of metastatic disease, will be imputed as follows:
 - No imputation will be done if the year is missing.
 - If the year is before informed consent date, then missing days will be imputed as the first day of the month and missing months will be imputed as July.
 - If the year is the current year of informed consent date, then missing days will be imputed as the first day of the month and missing months will be imputed as January.
- For time since initial diagnosis to randomization, partial dates will be imputed as follows:

- No imputation will be done if the year is missing.
- If the year is before randomization date, then missing days will be imputed as the first day of the month and missing months will be imputed as July.
- If the year is the current year of randomization date, then missing days will be imputed as the first day of the month and missing months will be imputed as January.
- For Prior or Concomitant Medication: Partial start or stop dates (where UN and UNK indicate unknown day and month respectively) will be imputed as follows:
 - Start dates:
 - UN-MMM-YYYY: Impute missing day as 01, so that CMs are assigned to prior and concomitant if there's any doubt.
 - DD-UNK-YYYY/UN-UNK-YYYY: If the year is before the year of first dose of study treatment, assume 01-JUL-YYYY of the collected year. If the year is after the year of first dose of study treatment, assume 01-JAN-YYYY of the collected year. If the year is the same as the year of first dose of study treatment and the stop date (after any imputation) is missing or is on or after the first dose of study treatment, then assume 01-JAN-YYYY, so that CMs are assigned to prior and concomitant. If the year is the same as the year of first dose of study treatment and the stop date (after any imputation) is prior to the first dose of study treatment, then assume the stop date for the start date.
 - Stop dates:
 - UN-MMM-YYYY: Assume the last day of the month.
 - DD-UNK-YYYY/UN-UNK-YYYY: Assume 31-DEC-YYYY.
 - In case of the death/study termination of the patients and the imputed stop date is after the date of death/study termination, the stop date will be imputed as the date of death/date of study termination.
 - Completely missing dates will not be imputed.
- For Post Anti-Cancer Therapies: Rules are as per concomitant medications above except when the imputed start date is earlier than the date of last dosing date, then the start date will be imputed as the date of last dosing date of study treatment + 1.
- For Adverse Events (missing month is not expected; missing day is allowed): Partial start or stop dates will be imputed as follows:
 - Partial start dates (where UN indicates unknown day):
 - UN-MMM-YYYY: If the month and year are different from the month and year of the first dose of study treatment, or the year is the same as the year of the first dose of study treatment, but the month is different, assume 01-MMM-YYYY. If the month and year are the same as the first dose of study treatment month and year and the end date (after any imputation) is missing or is on or after the first dose of study treatment, then assume the date of the first dose of study treatment. If the month and year are the same as the first dose of study treatment month and year and the end date (after any imputation) is prior to the first dose of study treatment, then assume 01-MMM-YYYY.

- Partial end dates (where UN indicates unknown day):
 - UN-MMM-YYYY: Assume the last day of the month.
 - In case of the death/study termination of the patients and the imputed end date is after the date of death/study termination, the end date will be imputed as the date of death/date of study termination.
- For OS with partial death date:
 - Every effort will be made to collect accurate death date. In case that the day is missing, the later date of the following will be used to calculate time to death:
 - first day of the month 01-MMM-YYYY, or
 - last visit date + 1, or
 - last known alive date + 1.
 - If day and month are both missing, the later date of 1st January of that year 01-JAN-YYYY, last visit date + 1, or last known alive date + 1 will be assumed when calculating time to death.
 - \circ If death date is completely missing then the later of last visit date + 1, or last known alive date + 1 will be assumed when calculating time to death.

Handling of missing data for analysis of PFS and QoL are described in the statistical analysis sections 8.1.1, 8.5.1 and 8.5.2.

